6.2 Identification of subjects

Subjects with a diagnosis of standard HER-2/neu-positive IBC or HER-2 2+ but FISH negative with Stage IIIA \geq N2, or have recurrent HER-2 positive metastatic breast cancer rendered NED by any means that have completed chemotherapy and/or trastuzumab will be recruited from the Rowan Breast Center. Up to 18 patients will be enrolled in this Pilot Phase I trial. No exceptions to eligibility will be made.

Fifteen subjects were enrolled at Rowan Breast Center.

Study Schema: Adjuvant HER2+

Inclusion Criteria

- 1. Women ≥ 18 years.
- Subjects with Invasive Breast Cancer at least Stage IIIA ≥ N2 (>4 positive nodes) or have recurrent metastatic breast cancer rendered NED by any means that are classic HER-2 3+ 10%, 2+ IHC and FISH positive or HER-2 2+ FISH negative that have completed chemotherapy and/or trastuzumab and have no evidence of disease.

Version v2 03/01/2017

Pilot Phase I HER-2 Pulsed DC Vaccine to Prevent Recurrence for Patients with HER-2 Driven High Risk Invasive Breast Cancer

- 3. Patients deemed to require anti-estrogen therapy for treatment of their breast cancer can continue anti-estrogen therapy during vaccinations
- 4. Women of childbearing age with a negative pregnancy test documented prior to enrollment.
- 5. Patients with ECOG Performance Status Score of 0 or 1 (Appendix D).

- 6. Women of childbearing potential must agree to use a medically acceptable form of birth control (medically accepted methods: birth control pills, condoms and spermicidal lubricants, intrauterine device, and diaphragm) during their participation in the study.
- 7. Subjects who have voluntarily signed a written Informed Consent in accordance with institutional policies after its contents have been fully explained to them.

Exclusion Criteria

- 1. Pregnant or lactating females.
- 2. Subjects with positive HIV or hepatitis C at baseline
- 3. Subjects with coagulopathies, including thrombocytopenia with platelet count <75,000, INR > 1.5 and partial thromboplastin time > 50 sec
- 4. Subjects with major cardiac illness MUGA < 50% EF.
- 5. Subjects with pre-existing medical illnesses or medications which might interfere with the study as determined by PI.

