6.5 Post-Vaccine Procedures

A. In vitro Immunologic testing

Subjects will have 5mL of peripheral whole blood drawn at multiple time points during the vaccine schedule (pre vaccine, post six vaccines, pre booster 1, pre booster 2, pre booster 3, and completion of all vaccinations) to monitor immunologic responses to the administered vaccines. Subjects will also have the option to undergo additional leukapheresis (10-15 liters) at the completion of the 6 vaccines or completion of the three boosters to obtain T lymphocyte population for additional immunologic analysis. The leukapheresis will be performed in the pheresis facilities at the University of Pennsylvania by certified personnel or at Moffitt Cancer Center, if needed. Attempts will first be made to obtain peripheral access for the pheresis protocol. Subjects will be pheresed 15-20 liters whole blood on a Gambro Spectra or equivalent apparatus. We expect to be able to generate $1-5 \times 10^{10}$ PBMC.

B. Post vaccine laboratory studies

In addition to the blood which will be drawn for the above analyses, an extra tube of serum will be drawn to test the subject's anti-HER-2/neu response. After boost vaccines additional 5 tubes of whole blood will be obtained for immune analysis. These results will be compared with the immune response results that will have been obtained prior to vaccination. An alternative post vaccine leukapheresis can be performed as alternative to blood draws.

- 1. After receiving their vaccines and prior to receiving boost vaccine series, subject will have the following completed:
 - a) CBC w/ differential
 - b) PT/PTT
 - c) electrolytes-Na/K/Cl/CO₂/BUN/Cr/glucose
 - d) liver function tests
 - e) urinalysis
 - f) MUGA or Echocardiogram (Compare to first study)

In addition to the blood drawn for the above analyses, 5 tubes of whole blood will be obtained for immune analysis and tube of serum will be drawn to test subjects anti-HER-2/neu response. These results will be compared with the immune response results that will have been obtained prior to vaccination.

In the event of abnormal symptoms, laboratory monitoring may be done earlier. The laboratory studies and intervals at which they are done will be determined by the PI on a case by case basis.

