6.9 Statistical Considerations

6.9.1 Design. A single arm phase I trial of HER-2 pulsed DC1 vaccine in subjects with high risk HER-2^{pos} breast cancer with residual disease after neoadjuvant therapy. Subjects will receive 6 weekly DC1 vaccinations and may then be eligible to receive up to 3 boost vaccinations given every 3 months. This study will enroll 18 evaluable subjects. Evaluable implies that a subject received all 6 weekly vaccinations and underwent leukapheresis after the vaccinations for immune response evaluation. Subjects will be followed for 30 days after their *final* vaccination.

6.9.2 Objectives. The primary objectives are to determine feasibility and safety. The secondary objectives are to evaluate immunogenicity and anti-HER2 immunity.

6.9.3 Endpoints. Feasibility is defined as a subject's ability and willingness to complete the treatment regimen (6 weekly vaccinations). Safety is established by grading the observed toxicities using CTC Version 3.0. Cardiac toxicity due to trastuzumab will be monitored 2 weeks after the sixth weekly vaccination (week 8) and at EOS and scored separately from vaccinerelated toxicity. Cardiac toxicity is defined as either asymptomatic change in MUGA (i.e., >20% decline in EF by repeat echo or EF <50%) or symptomatic EF drop or heart failure. Doselimiting toxicity (DLT) due to vaccination is defined as: Grade 2 allergic reaction/generalized urticaria, > Grade 3 allergic reaction/other, > Grade 2 autoimmune reaction, > Grade 2 cardiac toxicity or as specified above, > Grade 3 hematologic and non-hematologic toxicity (except fever) and > Grade 2 toxicity due to leukapheresis. DLT rate will be defined by the weekly vaccination schedule. Toxicities will be scored separately for the maintenance boost schedule. Immunogenicity is evaluated with descriptive statistics and box plots for multiple CD4+ and CD8+ T cell metrics obtained at baseline, 2 weeks after the sixth weekly vaccination (week 8) and after each maintenance boost, as show in the table below. Immune response (IR) is defined as >2 fold increase relative to baseline. Anti-HER2 response will be a quantitated by dilution studies. Long-term anti-HER2 immunity will be assessed at follow-up visits (e.g., q 6 months).

Immune Parameter	Assay Method	Fold change	Response (>2 fold ↑)
Peptide specific reactivities	Tetramer	~	\checkmark
CD8+ T cell activation or tumor recognition	cytokine release	~	\checkmark

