CD4+ T cell activation	ELISPOT	~	\checkmark
Overall immune response	(response to any of a	above)	

6.9.4 Monitoring Unacceptable Toxicity. Early termination rules for asymptomatic and symptomatic cardiac toxicity and vaccine-related dose-limiting toxicity have been defined for monitoring purposes. Toxicity data will likely be reviewed after groups of 3 women have been treated. Enrollment will be terminated if data indicate that the rate of 1) asymptomatic cardiac toxicity >20%, 2) symptomatic cardiac toxicity/heart failure >5% or 3) vaccine-related DLT rate >25%. For cardiac toxicity, we assume an uninformative beta (1, 1) prior and for vaccine-related DLT we assume a modestly informative beta (1, 3) prior since safety of our DC1 vaccine has been established in >50 women treated on our DCIS trials. Given the prior and the observed data, the Bayesian posterior probability that the toxicity rate exceeds the specified rate, is calculated. If the numbers of subjects with toxicity equals or exceeds the numbers (in shaded rows) in the table below, then it is likely that the toxicity rate is unacceptable, as noted by Bayesian posterior probabilities.

Bayesian Early Termination Rules for Cardiac Toxicity Rate							
Subjects treated	3	6	9	12			
Subjects with asymptomatic cardiac toxicity	1	2	3	4			
Bayesian Posterior Prob[tox rate >20%]	0.82	0.85	0.88	0.90			
Subjects with symptomatic cardiac toxicity/heart failure	1	1	1	1			
Bayesian Posterior Prob[tox rate >5%]	>0.9	>0.9	0.91	0.86			

Subjects with vaccine-related DLT	2	3	4	5
Bayesian Posterior Prob[DLT rate >25%]	0.83	0.83	0.84	0.85
Action	Terminat	te accrual	, re-evalu	ate trial

6.9.5 Statistical Analyses and End of Trial Decision-making. Feasibility. A narrative of reasons why subjects could not complete treatment will be written. Safety. All graded toxicities will be tabled and described by frequency and percentage. Attribution to DC1 vaccine or trastuzumab will be assigned, if possible. All cardiac toxicities will be reported in detail. Toxicities observed during weekly vaccination will be tabled separately from toxicities observed during maintenance boosts. **Immunogenicity**. Immunogenicity will be evaluated by descriptive statistics, plots of pre- and post-treatment values and fold changes. Immune response rate and 95% exact confidence interval will be calculated. Anti-HER2 response will be quantitated as EOS/baseline fold change in dilution studies.

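### The plan does not settle whether a cardiac event judged vaccine-related counts under the cardiac stopping rows, the vaccine DLT row, or both, because 6.9.3 attributes cardiac toxicity to trastuzumab and 6.9.4 does not

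*Combined protocol and SAP*

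**What the plan says.** The design in 6.9.1 is "A single arm phase I trial of HER-2 pulsed DC1 vaccine in subjects with high risk HER-2^{pos} breast cancer", so there is no comparator. Section 6.9.3 introduces the monitored cardiac endpoint with "Cardiac toxicity due to trastuzumab will be monitored 2 weeks after the sixth weekly vaccination (week 8) and at EOS", and the sentence continues "and scored separately from vaccinerelated toxicity". The definition that follows has no causal condition: "Cardiac toxicity is defined as either asymptomatic change in MUGA", or a symptomatic EF drop or heart failure. Later in the same paragraph, the list of DLTs caused by vaccination includes cardiac toxicity, either by grade or by reference back to that definition.

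Section 6.9.4 sets three termination rules: asymptomatic cardiac toxicity above 20%, symptomatic cardiac toxicity or heart failure above 5%, and vaccine-related DLT above 25%. Only the third carries a causal qualifier. Section 6.9.5 adds "Attribution to DC1 vaccine or trastuzumab will be assigned, if possible" and gives no criteria.

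On exposure, the inclusion criteria in 6.2 admit subjects "that have completed chemotherapy and/or trastuzumab and have no evidence of disease". Section 1.0 notes that HER-2 2+ FISH-negative patients are not usually treated with trastuzumab. Sections 6.7 A and 7.0 B describe trastuzumab as prior treatment and say the vaccine has not been given before to people who had received it. Section 6.7 D takes another line: it pools toxicity as arising from the vaccine process and sets the cardiac DLT at Grade 3 or above.

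On measurement, 6.9.3 describes the asymptomatic event as "asymptomatic change in MUGA (i.e., >20% decline in EF by repeat echo or EF <50" percent. Section 6.3 B allows either method at baseline, and 6.5 B lists "MUGA or Echocardiogram (Compare to first study" afterwards.

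**The concern.** Safety is a primary objective, and the termination table is the plan's formal protection. A stopping rule needs a numerator that two people would count the same way. Here one paragraph places cardiac toxicity outside vaccine-related toxicity and then inside the vaccine DLT list. For a subject who never received trastuzumab, the label in 6.9.3 cannot apply. If the label governs, that subject's cardiac event has no place in the cardiac rows.

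The rows are not equally strict. If a cardiac event judged vaccine-related were counted only as a DLT, it would face a looser boundary and a prior that already favours safety. The judgement would rest on an attribution with no criteria, no comparator and no earlier data in trastuzumab-treated subjects.

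The measurement wording raises a smaller, separate issue. If baseline and follow-up EF may come from different methods, a difference between methods can look like a change in the subject. One asymptomatic event among the first three subjects meets the boundary.

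**Working it through.** **1. Reproduce the table in 6.9.4.** With a Beta(a, b) prior and x events in n subjects, Pr(rate > r) is the upper tail beyond r of Beta(a + x, b + n − x). Section 6.9.4 gives Beta(1,1) for the cardiac rows and Beta(1,3) for the DLT row.

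| Row | Events at n = 3, 6, 9, 12 | Plan | Recomputed |
|---|---|---|---|
| Asymptomatic, r = 20% | 1, 2, 3, 4 | 0.82, 0.85, 0.88, 0.90 | 0.819, 0.852, 0.879, 0.901 |
| Symptomatic, r = 5% | 1, 1, 1, 1 | >0.9, >0.9, 0.91, 0.86 | 0.986, 0.956, 0.914, 0.865 |
| Vaccine-related DLT, r = 25% | 2, 3, 4, 5 | 0.83, 0.83, 0.84, 0.85 | 0.831, 0.834, 0.842, 0.852 |

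All twelve entries agree. The arithmetic of the table is sound; only the definition of what is counted is in question.

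**2. What one event does in each row.** One symptomatic event meets the symptomatic boundary at every look. The same event counted only as a DLT gives Pr(DLT rate > 25%) of 0.53, 0.30, 0.16 and 0.08 at 3, 6, 9 and 12 subjects, and stopping then needs 2, 3, 4 or 5 events. For asymptomatic events the boundaries are 1, 2, 3, 4 against 2, 3, 4, 5, a difference of one at each look.

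**3. Probability of stopping by 12 subjects.** Inputs are the boundaries above, looks after each group of three, independent subjects, one type of cardiac event at a time, and no other DLTs. The true rates are assumptions.

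- Symptomatic row: 1 − (1 − p)^12. At p = 10%, 1 − 0.9^12 = 0.718.
- Asymptomatic row at 10%: the first look contributes 1 − 0.9^3 = 0.271, and exact recursion over the later looks brings the total to 0.299.
- DLT row at 10%: the first look contributes 3 × 0.1² × 0.9 + 0.1³ = 0.028, and the total is 0.039.

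| Assumed true rate | Counted in symptomatic row | Counted in asymptomatic row | Counted only as DLT |
|---|---|---|---|
| 5% | 46% | 15% | 1% |
| 10% | 72% | 30% | 4% |
| 20% | 93% | 58% | 19% |

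If half of the events are moved to the DLT row at a true rate of 10%, the probabilities are 0.465 (symptomatic) and 0.158 (asymptomatic).

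**4. If events count in both rows.** Under these inputs, counting a cardiac event in its own row and also as a DLT leaves the cardiac-row figures unchanged, because the DLT boundary is higher than either cardiac boundary at every look.

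**5. The DLT grade.** Section 6.7 D gives Grade 3 or above. Section 6.9.3 prints > Grade 2, or the definition given earlier in the paragraph. Read literally on an integer scale, > Grade 2 is the same as Grade 3 or above, but the added definition still brings in asymptomatic EF changes that 6.7 D does not mention. The same list prints > Grade 2 for autoimmune and leukapheresis toxicity where 6.7 D has greater than or equal to, so the symbol may be a lost ≥; the grades would then differ too. The two sections do not agree on either reading.

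**The case against.** The strongest reply is that 6.9.4 already counts everyone. Its two cardiac rows, and the definition in 6.9.3, carry no causal condition, while the third row says vaccine-related. The authors used a qualifier where they wanted one. The cross-reference in the DLT list then suggests that an event counts in both places, and nothing says that a DLT leaves the cardiac row. Attribution appears in 6.9.5, which concerns reporting, and the committee in 6.6 E reviews toxicity assignments and may recommend suspension or termination. On this reading no stopping probability changes.

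Much of that stands. A reader might infer that attribution decides whether one event or several stop the trial. The documents do not support this: it follows only if the 6.9.3 label carries into the 6.9.4 counts, and several events applies only to symptomatic toxicity. A reader might also infer that no subject can be on trastuzumab, but the and/or wording in 6.2 does not expressly exclude continuing use.

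The reply does not remove the conflict. Section 6.9.3 is where the monitored endpoint is introduced, and it does so under the trastuzumab label and apart from vaccine toxicity. No sentence says which passage governs. The committee can catch a misplaced event, but its discretion does not define the count.

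On measurement, 6.5 B asks for comparison with the first study and allows a repeat scan after a significant decline. Neither requires the same method.

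**Conclusion.** The point holds as a conflict over a stopping-rule numerator. If the 6.9.4 wording governs, the effect is nil. If the 6.9.3 label governs, the symptomatic boundary moves from 1 event to 2-5 and the asymptomatic boundary by one event per look. The fall from 72% or 30% to 4% is the extreme case: an assumed true rate of 10%, every cardiac event moved to the DLT row, and no other DLTs. It is not an expected effect.

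The measurement point is qualitative only. A reader might want a rate of false EF events from switching methods, but the documents give no between-method variability, no baseline EF distribution and no frequency of switching.

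Sections 2.0 and 6.2 report fifteen subjects already enrolled, while the table ends at 12 treated. Enrolled is not treated, but some looks may have passed. The clarification would then also matter for how those looks are read.

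**What to change.** In 6.9.3, delete the attribution of cardiac toxicity to trastuzumab and the clause on separate scoring. In 6.9.4, state that the cardiac rows count every on-study cardiac event regardless of attribution, and that such an event also counts as a DLT when it meets the DLT definition. Keep attribution in 6.9.5 for description only. Reconcile the cardiac DLT threshold between 6.7 D and 6.9.3, since the double-counting sentence depends on it. If any look has already taken place, record which counting convention was used.

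Separately, require each subject's follow-up and confirmatory EF to use the same method as the baseline measurement, and correct the wording in 6.9.3 that judges a change in MUGA by echocardiogram.

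The cost is mainly wording. Slightly more events may count toward stopping, and scheduling becomes a little less flexible for subjects who transfer between sites.

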Between 8 and 21 days post vaccine the patient will return for the sixth vaccination. Again a history and physical exam will be taken. Any changes in history or physical will be documented. Ultrasound (US) guided intranodal delivered vaccines will be administered in the NIH Clinical Research Center at Penn or the Clinical Research unit at Moffitt Cancer Center by a radiologist or sonographer experience in ultrasound guidance and the principal investigators or his/her designee.

Each dose will consist of between $1.0-2.0 \times 10^7$ cells and will be injected into 1-2 different normal groin lymph nodes or axillary nodes.

O. Post vaccine assessment

Subjects will be administered the vaccines and observed. All subjects with vaccine related AEs will be followed until the AE has resolved to baseline. Vital signs will be obtained prior to the vaccination and again 15 minutes after the dose is given. Subjects with no noted complications will then be discharged. The anticipated complication could be fever. If an Adverse Event is observed, the subject observation time will be revised appropriately. A physician familiar with the study will be readily available in the event of any complication and such subjects will be transferred to an appropriate care unit for further monitoring and treatment. Similarly any discharged subject who develops symptoms will be promptly re-evaluated and admitted for care if inpatient hospitalization is deemed necessary by the PI or his/her designees.

P. Administration of Additional Boost Vaccines.

After the subject has completed 6 vaccines, they will undergo leukapheresis to obtain lymphocyte and monocyte fractions, if needed.

Q. Administration of First Boost Vaccine

Approximately 3 months from completion of the induction vaccines, subjects will receive 3 boost vaccines at approximately 3 month intervals. Again a history and physical exam will be taken. Any changes in history or physical will be documented. Ultrasound (US) guided intranodal delivered vaccines will be administered in the NIH Clinical Research Center at Penn or the Clinical Research unit at Moffitt Cancer Center by a radiologist or sonographer experience in ultrasound guidance and the principal investigators or his/her designee. Each dose will consist of between $1.0-2.0 \times 10^7$ cells and will be injected into 1-2 different normal groin lymph nodes or axillary nodes

R. Post vaccine assessment

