If significant decline in EF was evident in pre/post vaccine MUGA scan or ECHO, another MUGA scan or ECHO may be performed 1 month post-vaccine, as determined by the PI. Subjects will be closely monitored by the PI, who will determine the need for additional MUGA scan(s) during the 6 month post-vaccine monitoring period on a case by case basis.

C. Long-term Follow-up

After completing the 6 month post-vaccine monitoring period, all subjects will be seen yearly. Mammograms will be obtained at yearly visits if patients have remaining breasts. For Version v2 03/01/2017 30 Pilot Phase I HER-2 Pulsed DC Vaccine to Prevent Recurrence for Patients with HER-2 Driven High Risk Invasive Breast Cancer mastectomy subjects a yearly mammogram of the contralateral breast. This will continue for 5 years.

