- **28.** Duru N, Fan M, Candas D, et al. HER2-Associated Radioresistance of Breast Cancer Stem Cells Isolated from HER2-Negative Breast Cancer Cells. *Clin Cancer Res.* Nov 16.

Pilot Phase I HER-2 Pulsed DC Vaccine to Prevent Recurrence for Patients with HER-2 Driven High Risk Invasive Breast Cancer Appendix 1 - Schedule of Assessments

Procedures	Baseline	Vaccin	Vaccine	Vaccine	Vaccine	Vaccine	Vaccine	Booster	Booster	Booster	EOT
	/ Pre	e 1	2	3	4	5	6	1	2	3	
	Vaccine										
Consent	Х										
Tumor Biopsy ¹	X										
Biomarkers ²	X										
Medical Hx	X	Х	Х	Х	Х	Х	Х	Х	Х	Х	
Vital Signs	X	X ³									
Physical Exam	X	Х	Х	Х	Х	Х	Х	Х	Х	Х	
Height	X										
Weight	X										
CBC w/diff	X							Х			
PT/PTT	X							Х			
СМР	X							Х			
Urinalysis	X							Х			
Pregnancy	v										
Test	л										
EKG	Х										
HLA	Х										
LVEF ⁴	Х							Х			
Immune	v							v	v	v	
Assays	Л							Л	Л	Л	
ECOG PS	Х										
Mammogram	Х										
CT/PET	X										
Ultrasound		Х	Х	Х	Х	Х	Х	Х	Х	Х	
AE		Х	Х	Х	Х	Х	Х	Х	Х	Х	Х
Leukapheresis	Х						X ⁵			X ⁵	

Procedures	FOLLOW UP					
	6 mos.	Y1	Y2	Y3	Y4	Y5
Consent						
Tumor Biopsy ¹						
Biomarkers ²						
Medical Hx	Х					
Vital Signs	Х					
Physical Exam	Х					
Height						
Weight						
CBC w/diff	Х					
PT/PTT	Х					
СМР	Х					
Urinalysis						
Pregnancy						
Test						

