EKG						
HLA						
LVEF ⁴						
Immune	v					
Assays	А					
ECOG PS						
Mammogram		Х	Х	Х	Х	Х
CT/PET						
Ultrasound						
AE						
Leukapheresis	X ⁵					

1. Core biopsy or excisional biopsy demonstrating IBC.

2. Biomarkers collected: ER, PR, HER-2/neu and FISH

3. Collect VS prior to injection and 15 (+/- 5 min) post injection

4. Subject is closely monitored and the need for additional LVEF during the 6 month post-vaccine monitoring period is determined on case-by-case basis.

5. Optional leukapheresis, done only if needed

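### Section 6.9.3 promises a cardiac assessment at an undefined EOS, and Appendix 1 schedules no LVEF after Booster 1, so asymptomatic cardiac toxicity cannot be systematically scored for the boost phase

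*Combined protocol and SAP*

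**What the plan says.** Section 6.9.3 sets two post-baseline readings: "Cardiac toxicity due to trastuzumab will be monitored 2 weeks after the sixth weekly vaccination (week 8) and at EOS". The asymptomatic part of the endpoint is an EF decline above 20% or an EF below 50%. The symptomatic part is a symptomatic EF drop or heart failure. Sections 6.9.3 and 6.9.5 keep boost-phase toxicity apart from weekly-phase toxicity, and 6.9.5 reports every cardiac toxicity in detail.

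EOS appears in 6.9.3, and again in 6.9.5 for the anti-HER2 fold change. Neither place defines it. Section 6.9.1 states "Subjects will be followed for 30 days after their" final vaccination, but does not call that point EOS.

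Section 6.5.B fixes one scan after baseline. "After receiving their vaccines and prior to receiving boost vaccine series, subject will have the following completed", and MUGA or echocardiogram is on the list that follows. After a significant decline, "another MUGA scan or ECHO may be performed 1 month post-vaccine, as determined by the PI". Beyond that it is the PI "who will determine the need for additional MUGA scan(s) during the 6 month post-vaccine monitoring period on a case by case basis".

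The table headed "Appendix 1 - Schedule of Assessments" marks LVEF at Baseline and Booster 1 only. Footnote 4 adds that "the need for additional LVEF during the 6 month post-vaccine monitoring period is determined on case-by-case basis".

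On boosts, Section 6.4.6 says: "Approximately 3 months from completion of the induction vaccines, subjects will receive 3 boost vaccines at approximately 3 month intervals".

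**The concern.** An asymptomatic EF decline exists in the data only if someone measures the EF. If the visit schedule is followed as printed, no subject has a required scan after any boost dose. The statistical section still promises a reading at EOS and a separate boost-phase toxicity table.

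Safety is a primary objective (6.9.2), and Section 6.7.A says that this vaccine had not been given before to Herceptin-treated patients, so earlier experience does not fill the gap. A boost-phase table with no asymptomatic cardiac toxicity could not separate a true absence from an absence of scans. Scans ordered at the PI's discretion would cover a selected group with no planned denominator.

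**Working it through.** **1. The plan's own figures.** For asymptomatic cardiac toxicity, 6.9.4 uses a beta(1, 1) prior, so the posterior after x events in n subjects is Beta(1 + x, 1 + n − x).

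- For 1 of 3 this is Beta(2, 3), and P(rate > 0.20) = 0.8⁴ + 4 × 0.2 × 0.8³ = 0.4096 + 0.4096 = 0.819 (plan: 0.82).
- For 2 of 6, 3 of 9 and 4 of 12 the same calculation gives 0.852, 0.879 and 0.901 (plan: 0.85, 0.88, 0.90).
- The 3-of-15 rule in 6.9.6 gives 0.764 at a true rate of 25% and 0.184 at 10% (plan: 0.76 and 0.18).

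These figures depend only on counts and numbers treated, and visit timing does not enter. The point concerns what is measured.

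**2. Promised readings against scheduled readings.**

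| Reading in 6.9.3 | Section 6.5.B | Appendix 1, LVEF row |
|---|---|---|
| 2 weeks after dose 6 | Allowed: one scan required between dose 6 and the boosts | No week-8 column; marked at Booster 1, together with the rest of the pre-boost panel |
| EOS (undefined) | No fixed scan; later scans at the PI's discretion | Blank at Boosters 2 and 3, EOT and 6 months; also blank at Years 1–5 |

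One of the two promised post-baseline readings has a place and one has none.

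**3. Whether the blank cells mean anything.** Alone they are weak evidence. Vital Signs, as extracted, is marked only at Baseline and Vaccine 1, although 6.4.6 requires vital signs at every dose. Here, however, the body text supplies no post-boost scan either: the one fixed post-baseline scan in 6.5.B is before the boosts, and the rest are conditional or discretionary. Nothing forbids a post-boost LVEF, but nothing outside 6.9.3 schedules one.

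**4. Length of the unscanned stretch.** Take 3 months as 91 days. Boosters 1, 2 and 3 then fall 91, 182 and 273 days after dose 6. Booster 1 to Booster 3 is 273 − 91 = 182 days with no scheduled LVEF, and none follows. If EOS is 30 days after Booster 3, that scan comes 91 + 30 = 121 days after Booster 2 and 2 × 91 + 30 = 212 days after Booster 1.

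**5. What is still captured.** AEs are marked at every booster and at EOT, and history and physical exam at every booster. Section 6.7.A requires monitoring for heart failure. The gap is confined to asymptomatic decline. The DLT rate is defined on the weekly schedule (6.9.3), so the boost-phase gap does not reach it.

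**The case against.** The best defence is that 6.9.3 is itself protocol text and already requires the EOS assessment, so the fault is only that Appendix 1 fails to carry it over. That stands as a description of the fault. It does not remove it, because without a definition of EOS a site cannot tell when to scan.

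The consequence can also fairly be called modest. Section 5.3 reports earlier EF declines of about 10% in about 10% of patients, all within normal range and back to baseline at a 30-day repeat. Such declines would not have met the 6.9.3 definition. Those patients had not just had chemotherapy or trastuzumab, so this is only partial reassurance.

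The label of the endpoint, cardiac toxicity due to trastuzumab, might suggest that boosts are irrelevant to it. But 6.9.5 assigns attribution only where possible and reports all cardiac toxicity, so the EF data are needed under either label.

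A reader might go further and infer from the Booster 1 column that the post-induction scan is also mistimed: about 13 weeks after dose 6 instead of 2, hence 11 weeks late. The documents do not establish this:

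- Week 8 lies inside the 6.5.B window.
- The Booster 1 column carries CBC, PT/PTT, CMP and urinalysis beside LVEF, which matches the 6.5.B panel.
- Appendix 1 has no week-8 column and ties other post-induction work to neighbouring visits; leukapheresis, for example, sits under Vaccine 6.
- The repeat scan at 1 month post-vaccine, counted from dose 6, makes sense only if the first scan came soon after dose 6.

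What remains of this is a request for a clear date.

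**Conclusion.** The point holds for the boost phase. EOS is undefined, Appendix 1 carries no LVEF after the pre-boost scan, and later scans are discretionary. Asymptomatic cardiac toxicity therefore cannot be systematically scored for the boost phase, although the plan commits to scoring and tabling boost toxicity separately. One of two promised post-baseline readings is unscheduled, and the boosts span about 182 days.

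This rests on reading the LVEF row from extracted text and on 91-day boost intervals.

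Two other inferences should be resisted. One is that EOS might lie about 5 years out. Section 6.9.1 ends follow-up 30 days after the final vaccination, and 6.9.3 mentions long-term follow-up visits separately, so 30 days is the most natural reading. The other is that the stopping rules are undermined. Every stated probability reproduces, and Section 2.0 records fifteen subjects already enrolled, past the last tabulated look at 12. The change is worth making because a primary safety endpoint cannot be delivered as written from this schedule; no error rate is at stake.

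**What to change.** Define EOS in 6.9.3 as 30 days after the final vaccination, consistent with 6.9.1, and enter in Appendix 1 the EOS LVEF that 6.9.3 already promises. Because 6.9.5 also uses EOS for the anti-HER2 fold change, check that the same definition suits that sample. For a subject who receives no boost, EOS would fall 30 − 14 = 16 days after a week-8 scan, so say whether one scan serves both.

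If the scan is not wanted, restate the 6.9.3 cardiac endpoint at the scheduled visits and state that boost-phase asymptomatic cardiac toxicity is not assessed.

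In either case, report boost-phase asymptomatic cardiac toxicity over the number of subjects scanned after a boost. This also serves subjects already past these visits.

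As a secondary clarification, date the post-induction LVEF in 6.5.B and Appendix 1 at 2 weeks after actual dose 6, so that the Booster 1 column is not taken as the scan date.

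The cost is text edits plus at most one scan per boosted subject, already promised in 6.9.3. Section 6.9.1 makes boosts conditional, so fewer than 18 subjects may need it. A single EOS scan, 121 and 212 days after Boosters 2 and 1 when three boosts are given, can still miss transient declines after those doses. Restating the endpoint adds no scans but gives up these data.
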